Based on our supportive pilot data, Aim 1 will test the hypothesis that wearing the MyoPro 2 Motion-G will result in the largest increases in UE movement compared to the resting hand splint and compared to no device as measured by the upper extremity section of the Fugl-Meyer Scale (UE FM); our primary outcome measure. While not a functional measure, per se, this measure is sensitive to all levels of UE impairment and is, thus, best situated to examine the changes in active UE movement likely to occur in the paretic UE that are hypothesized to occur most prominently with MyoPro 2 Motion G use. Further, functional outcomes are rigorously assessed using the battery of assessments described in Aim 2.

**Specific Aim 2: Determine the impact of the MyoPro 2 Motion G myoelectric brace on affected UE outcomes.** All subjects will undergo a battery of assessments to compare the impact on UE outcomes when utilizing the MyoPro 2 Motion G, resting hand splint and no device as explained above. Each subject will be administered (a) a battery of functional tasks; (b) the Box and Block (B&B) Based on our supportive pilot data, Aim 2 will test the hypothesis that wearing the MyoPro 2 Motion G will result in the largest increases in UE outcomes compared to the splint and compared to no device.

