**Data Analyses**

**Power and Sample Size Justification:**

For the past 9 months, members of the study team have collected data comparing the effect of wearing the MyoPro Motion G versus not wearing the MyoPro Motion G on UE movement in moderately impaired stroke survivors. This work showed a mean change of 8.72 ± 7.1 points on the UE FM when subjects wore the MyoPro Motion G (Table 3). From this work, we have formed the primary study hypothesis, which is that subjects will exhibit significantly higher scores on the UE FM when using the MyoPro 2 Motion G compared to scores when using the splint and no device.

**Table 3:** Pilot Data Leading to the Current Trial

condition	Method	Mean	99% CL Mean		Std Dev	99% CL Std Dev		99% UMPU CL Std Dev	
with		27.2778	21.9152	32.6403	7.8501	5.4157	13.5603	5.3232	13.2488
without		18.5556	14.2528	22.8583	6.2987	4.3454	10.8803	4.2712	10.6304
Diff (1-2)	Pooled	8.7222	2.2498	15.1947	7.1168	5.4042	10.2156	5.3562	10.1038
Diff (1-2)	Satterthwaite	8.7222	2.2318	15.2127					

Method	Variances	DF	t Value	Pr >  t
Pooled	Equal	34	3.68	0.0008
Satterthwaite	Unequal	32.475	3.68	0.0008

[figure not shown]
Equality of Variances				
Method	Num DF	Den DF	F Value	Pr > F
Folded F	17	17	1.55	0.3729

Based on the above work, we have taken a very conservative estimate of effect size (Table 4), and estimate that a sample size of  $n=49$ , will provide approximately 80% power to detect a medium effect size of  $f=0.2521$  when alpha is set to 0.05 for repeated measures MANOVA with 1 group and 3 measurements, using the  $F$ -distribution. (Figure 2). Given a liberal attrition rate of 20% and the need to examine age-associated differences in depth (i.e., covariates such as age and time since stroke), we plan to enroll up to a total of 75 participants ( $n = 75$ ) to ensure adequate power for the planned analyses.

**Table 4:** Point Estimate and 95% Confidence Interval Effect Size,  $d$  and  $f$

	Effect Size		
	Point Estimate	95% Lower Bound	95% Upper Bound
$d$	1.22667	0.50413	1.93409
$f$	0.6134	0.2521	0.9670

**Figure 2:** Differences Between Independent Means and Power/Sample Size Estimates

"Functional Assistance provided by Myoelectric Elbow-wrist-hand orthoses" (FAME)

Desired Power	Required Sample Size
0.600000	32.393509
0.610000	33.035972
0.620000	33.689708
0.630000	34.355391
0.640000	35.033746
0.650000	35.725556
0.660000	36.431665
0.670000	37.152989
0.680000	37.890523
0.690000	38.645352
0.700000	39.418662

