**Data Analyses:**

**Primary Study Hypothesis:** Subjects will exhibit significantly higher scores on the UE FM when using the MyoPro 2 Motion G compared to scores when using the splint and no device.

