**Secondary Study Hypotheses:**

**Hypothesis 2a:** Subjects will exhibit significantly higher scores on the B&B when using the MyoPro 2 Motion G compared to scores when using the splint and no device.

**Hypothesis 2b:** Subjects will exhibit significantly higher quality scores and decreased time on the battery of functional tasks when using the MyoPro 2 Motion G compared to scores when using the splint and no device.

We will evaluate primary and secondary study hypotheses using repeated measures MANOVA. The independent variable is device usage and has three levels: (1) performance with MyoPro 2 Motion G, (2) performance with the resting hand splint, and (3) performance without device. The multiple dependent variables include: (1) UE movement as measured by the UEFM (primary hypothesis), (2) dexterity as measured by the B&B (hypothesis 2a), and (3) functional movement as measured by the novel battery (hypothesis 2b). A significant main effect and/ or interaction effect will be investigated in greater detail using univariate tests. These analyses are powered to permit inclusion of 1-2 covariates such as participant age and time since stroke. Post-hoc analyses will include a specific contrast for participants aged 65 and over.

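### The primary hypothesis needs MyoPro to beat both the splint and no device on UE FM, but the planned test and the stated 80% power address only whether the three conditions differ at all

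*Protocol*

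**What the plan says.** Specific Aim 1 predicts that the MyoPro "will result in the largest increases in UE movement compared to the resting hand splint and compared to no device". The primary hypothesis under Data Analyses repeats this: UE FM scores are to be significantly higher "when using the MyoPro 2 Motion G compared to scores when using the splint and no device".

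The analysis paragraph, under Secondary Study Hypotheses, assigns one method to the primary and secondary hypotheses together. It is a repeated measures MANOVA with a three-level device factor and several outcomes, beginning "The multiple dependent variables include: (1) UE movement as measured by the UEFM (primary hypothesis" and going on to Box and Block and the functional battery. The follow-up is: "A significant main effect and/ or interaction effect will be investigated in greater detail using univariate tests". The only contrast named there concerns participants aged 65 and over.

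Power and Sample Size Justification gives about 80% power at n=49, with f=0.2521 and alpha 0.05, "for repeated measures MANOVA with 1 group and 3 measurements". Enrolment is then raised to as many as 75, allowing for 20% attrition and covariates, "to ensure adequate power for the planned analyses". The effect size comes from a pilot of "the effect of wearing the MyoPro Motion G versus not wearing the MyoPro Motion G", and of it the section says "we have taken a very conservative estimate of effect size".

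**The concern.** A significant device effect says that the three conditions are not all alike. It does not say which differ, or in which direction. It can arise because the splint hinders movement, because MyoPro beats only one comparator, or because MyoPro is worse. It therefore cannot by itself support the hypothesis as worded.

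The named follow-up does not clearly close the gap. After a MANOVA on several outcomes, univariate tests normally means one test per outcome, which for UE FM is still a 2-df test across three conditions. The follow-up also depends on a joint test that includes secondary outcomes.

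The power statement has the same mismatch. It gives the chance of detecting any difference on one outcome, not the chance of confirming the hypothesis. The pilot had no splint condition, so nothing is assumed about where the splint lies, yet that position decides the MyoPro-versus-splint comparison.

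**Working it through.** **Inputs from the protocol.** f=0.2521; alpha 0.05; three conditions; the power table (for example n=48.538415 at 0.80); enrolment up to 75, hence 75 × 0.80 = 60 completers. Table 4 gives d=1.22667 with lower bound 0.50413, and 0.50413/2 = 0.2521, so f is a two-condition conversion of the pilot's lower bound.

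**Reproducing the stated power.** For a one-group repeated measures MANOVA with three measurements, power comes from a noncentral F with df 2 and n−2 and λ = 3·n·f²/(1−ρ). The correlation ρ is not stated. Taking ρ=0.10 gives, at n=48.538415, λ = 3 × 48.538415 × 0.06355/0.90 = 10.28 and power 0.800. The tabled n of 32.393509, 62.784876 and 75.947367 return 0.600, 0.900 and 0.950. The table is therefore a 2-df omnibus test with an implied ρ of 0.10. A single comparison (1 df) does not fit it.

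**Condition means that give f=0.2521.** Here f is the SD of the three means (divisor 3) in within-condition SD units.
- Splint equals no device, means (δ, 0, 0): SD = δ√2/3, so δ = 0.2521/0.4714 = 0.535.
- Splint midway, means (δ, δ/2, 0): SD = δ/√6, so δ = 0.2521/0.4082 = 0.618, and MyoPro minus splint is 0.309.
- MyoPro equals no device, splint worse: (0, −0.535, 0).

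**Each comparison.** For a paired t test at two-sided 0.05 the standardised effect is the difference divided by √(2(1−ρ)), which is √1.8 = 1.342 at ρ=0.10. At n=49:
- Splint equals no device: 0.535/1.342 = 0.399, noncentrality 0.399 × 7 = 2.79, power 78% for each comparison.
- Splint midway: 35% against the splint and 88% against no device.

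**Both comparisons significant in MyoPro's favour**, simulated with equal variances and a common correlation, ρ=0.10:

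| n | Omnibus | Both: splint = no device | Both: splint midway | Both: MyoPro = no device, splint worse |
|---|---|---|---|---|
| 49 | 80% | 66% | 34% | about 2.5% |
| 60 | 88% | 77% | 41% | about 2.5% |
| 75 | 95% | 87% | 50% | about 2.5% |

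Omnibus power is the same in every pattern because f is fixed. At n=49 the omnibus test is significant without both comparisons being won in 16% of trials (splint equals no device) and 47% (splint midway).

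**Sensitivity to ρ**, both comparisons:

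| ρ | n=60, splint = no device | n=60, midway | n=75, splint = no device | n=75, midway |
|---|---|---|---|---|
| 0.1 | 77% | 41% | 87% | 50% |
| 0.2 | 83% | 46% | 91% | 55% |
| 0.3 | 88% | 51% | 95% | 61% |
| 0.5 | 97% | 65% | 99% | 75% |

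Completers needed for 80% on both when the splint equals no device: 64, 57, 51 and 37 at these four correlations. With the splint midway and ρ=0.10, about 150.

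**Sensitivity to effect size.** At the pilot point estimate (d=1.227 against no device, ρ=0.10), joint power is about 100% if the splint equals no device. With the splint midway it is 88%, 94% and 97% at n=49, 60 and 75.

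**The case against.** The term univariate tests is ambiguous and does not exclude pairwise comparisons. The protocol mentions post-hoc contrasts, without an exhaustive list, and the SAP, which is not at hand, may define the two comparisons. An omnibus test followed by pairwise tests is a recognised procedure, and a gate on UE FM alone costs little: at n=60 and ρ=0.10, joint power falls from 77.0% to 76.3%.

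The low figures also rest on assumed scenarios. They combine a deliberately conservative f, a low correlation for repeated scores on one scale within three weeks, and a splint placed exactly midway, which nothing in the protocol supports. In that pattern MyoPro minus splint is 0.309 × 7.1 = 2.2 UE FM points, against a pilot gain over no device of 8.72. At an assumed ρ of 0.7, joint power at n=60 is 99.9% (splint equals no device) or 86% (midway). The case with MyoPro equal to no device runs against the pilot's 99% interval of 2.25 to 15.19 points, obtained with an earlier device version.

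Most of this stands as a limit on size. The scenarios show what the stated power leaves open; they do not predict the result. The mismatch itself remains. Even if univariate tests are read as pairwise, neither comparison is named and the 80% does not describe them. The protocol itself assigns the test and states the power, whatever the SAP adds. The UE FM gate is harmless, but the protocol's gate is a joint test over several outcomes.

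**Conclusion.** The concern holds and should be fixed. The protocol assigns a non-directional, multi-outcome omnibus test to a directional hypothesis with two comparators, and its 80% is power for the omnibus question on one outcome. At the plan's own f and the inferred correlation of 0.10, the chance of confirming the hypothesis falls short of omnibus power by 11 percentage points at 60 completers if the splint equals no device (88% against 77%), and by 47 points if it lies midway (88% against 41%).

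The mismatch is certain; the size of the shortfall is not. It depends on a correlation and a splint position that the protocol does not give, and it shrinks or disappears at higher correlations or at the pilot effect. Nothing here shows that enrolling 75 is too few.

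**What to change.** Make UE FM alone the primary analysis, with two named within-subject contrasts: MyoPro minus splint, and MyoPro minus no device. Test each at two-sided 0.05 and declare the hypothesis confirmed only if both are significant in MyoPro's favour. Because both must succeed, no alpha split is needed. An omnibus test on UE FM may stay, but the contrasts should not depend on the joint multi-outcome MANOVA. Restate power for winning both contrasts at 60 to 75 evaluable subjects, and write down the assumed correlation and splint-versus-no-device difference.

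The change itself needs protocol wording and a new calculation, with no extra data or visits. The price is a less favourable figure: 77% rather than 88% at 60 completers if the splint equals no device and ρ=0.10. If the team thinks a midway splint plausible at the lower-bound effect, the figure is 41%, and 80% would need about 150 completers. A result that beats only one comparator would no longer confirm the hypothesis.

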**Secondary Outcome Measures (Aim 2):**

- Demonstration of orthotic-assisted increases in motor ability alone is not sufficient to warrant clinical use of a device. Indeed, increases in orthotic-assisted UE movement must translate into improvements in functional outcomes. Additionally, the MyoPro 2 Motion G provides full active assisted ROM at the elbow to facilitate increased ability to carry out proximally-based functional tasks. While useful in assessing distal functional abilities, many distally based measures may not fully quantify an increased ability to carry out more proximally-based, gross motor tasks involving the elbow.

As such, investigators will administer a battery of proximally-based, commonly-performed *functional tasks* (ICF: activity). This battery was used in our preliminary work leading to the current application, and consists of: (a) stabilizing a mixing bowl while stirring, (b) simulated drinking, (c) picking up a laundry basket, (d) putting an item in a laundry basket, (e) opening deodorant, (f) opening a pill bottle, (g) cutting a block of cheese, and (h) sweeping. Quality of movement on each task and sub-task will be rated using a 6-point ordinal scale (0=performs no part of task, does not attempt with the affected arm; 5=performs normally) and performance of each task will be timed, with 60 seconds allotted for each subtask. This battery will provide valuable information regarding proximal and gross distal functional abilities as well as speed of task completion.

Importantly, in pilot work leading to this study, our sample size was not large enough to fully determine the battery’s psychometrics, but internal consistency was demonstrated. While not a primary aim of this study, the study biostatistician will perform full psychometric analyses to determine the measurement properties of this instrument, as described later.

- The *Box and Block Test (B&B)* (ICF: activity) is suggested to determine whether changes occur in UE *gross manual dexterity*. During the test, the subject is seated in front of a wooden box with a partition in the middle, and is asked to move colored blocks from one side of the box, over the partition, to the other side. The number of blocks moved in one minute is recorded. The test’s test-retest reliability and validity have been shown in stroke.

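### The joint MANOVA that precedes the univariate tests can be made significant by UE FM alone, so it gives Hypotheses 2a and 2b no familywise protection when the primary outcome succeeds

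*Protocol*

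**What the plan says.** The analysis paragraph under Secondary Study Hypotheses in the Protocol evaluates the primary and secondary hypotheses together by repeated measures MANOVA. The factor is device use with three levels: MyoPro, splint and no device. The dependent variables listed are UE FM (primary), Box and Block (2a) and the functional battery (2b). The next step is: "A significant main effect and/ or interaction effect will be investigated in greater detail using univariate tests". One or two covariates, such as age and time since stroke, may be included.

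Hypotheses 2a and 2b are both worded as the device beating the splint and no device. Hypothesis 2b names two results from the battery, higher quality and shorter time. The protocol gives no testing order, no alpha for the univariate tests and no multiplicity rule.

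The only alpha is in Power and Sample Size Justification, where n = 49 "will provide approximately 80% power to detect a medium effect size of" f = 0.2521 "when alpha is set to 0.05 for repeated measures MANOVA with 1 group and 3 measurements". Secondary Outcome Measures (Aim 2) explains why the functional outcomes were added: "Demonstration of orthotic-assisted increases in motor ability alone is not sufficient to warrant clinical use of a device".

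**The concern.** Following a significant MANOVA with univariate tests is often taken to control the error across outcomes. It does so only under the complete null, where no outcome differs between conditions. Here the primary outcome is one of the dependent variables and is expected to differ: the pilot showed a "mean change of 8.72 ± 7.1 points on the UE FM". If UE FM differs, the joint test tends to be significant whatever Box and Block and the battery do, and the univariate tests on those outcomes then run with no protection from it.

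There is a second weakness. A univariate test of a three-level factor asks whether any two conditions differ. It can be significant because the splint differs from no device, which supports neither 2a nor 2b.

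By the protocol's own account, the functional outcomes are what turns a movement gain into a case for clinical use. They lose protection when the primary outcome succeeds, which is when they will be read.

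**Working it through.** **Inputs from the Protocol.** Alpha is 0.05, n = 49 and f = 0.2521 (Power and Sample Size Justification). Table 4 gives f = 0.6134 as the point estimate and 0.2521 as the lower 95% bound. Enrolment is up to 75 with 20% attrition, so 75 × 0.8 = 60 completers. The joint test has K = 3 outcomes (battery as one) or K = 4 (quality and time separate).

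**Assumptions.** The correlation between outcomes is not given and is taken as 0 to 0.7. The within-subject correlation is not given either. Step 1 infers 0.1 for the planning calculation. The simulations with a 0.5-1 SD effect use 0.5.

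**1. The plan's own figure.** Use a noncentral F with df (2, N − 2) and λ = N × f² × 3/(1 − ρ).
- With ρ = 0.1, λ per participant = 0.2521² × 3/0.9 = 0.2118.
- 80% power then needs N = 48.538, which matches the table's 48.538415. Power at n = 49 is 0.804.
- ρ = 0 would give 53.6 and ρ = 0.5 would give 28.4.

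The figure is reproduced. Its 2 numerator df belong to one outcome measured three times, not to the joint test of three or four outcomes.

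**2. How often UE FM alone makes the joint test significant.** Use F with df (2K, n − 2K) and the same λ, with uncorrelated outcomes and no effect on the secondaries.

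| UE FM effect | n | λ | K = 3 | K = 4 |
|---|---|---|---|---|
| f = 0.2521 | 60 | 60 × 0.2118 = 12.71 | 71% | 64% |
| f = 0.2521 | 75 | 75 × 0.2118 = 15.89 | 83% | 77% |
| f = 0.6134 | 60 or 75 | | 100% | 100% |

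Simulation at n = 60 with a UE FM effect of 0.5 to 1 SD gives 87% to 100%. Correlation between outcomes raises the figure: at f = 0.2521, simulations over n = 60 and 75 and correlations 0 to 0.6 gave 66-98%.

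**3. False univariate omnibus tests when UE FM has an effect and the secondaries have none.** If the joint test is always significant and the m outcomes are independent, the chance of at least one false result is 1 − 0.95^m.
- Two outcomes (Box and Block, battery): 1 − 0.95² = 9.75%. Simulated: 9.6%, 9.4% and 8.5% at correlations 0, 0.5 and 0.7.
- Three outcomes (Box and Block, quality, time): 1 − 0.95³ = 14.3%. Simulated: 13.9%, 12.8% and 11.3% at the same correlations. Other runs reached 15%; the excess over 14.3% is simulation error.
- Any single outcome, for example Box and Block: about 5%.
- At f = 0.2521 with three outcomes: still about 13%, although the joint test is significant less often. A chance difference in a secondary outcome itself helps to make the joint test significant.

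**4. The complete null.** With no UE FM effect (K = 4, correlation 0.5), the joint test is significant in 5.1% of trials and any false secondary omnibus test occurs in 3.1%. The joint test does its job only here.

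**5. The claim as 2a and 2b are worded.** Suppose a claim requires two-sided p < 0.05 in the device's favour against both comparators. With no effect, a false claim arises in 0.3-0.6% of trials for Box and Block and 0.8-1.5% for any secondary outcome. In the least favourable case the device truly beats one comparator only. Each outcome then has error 2.5%, which gives 1 − 0.975² = 4.9% for two outcomes and 1 − 0.975³ = 7.3% for three.

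**The case against.** The strongest reply is that the protocol never says the follow-up tests are unadjusted. Multiplicity among secondary outcomes is commonly left to the SAP, which is not shown and could add an adjustment without contradicting the protocol. That stands, so the 9-15% is conditional on nothing being added. It does not remove the point, because the protocol does state a procedure, and the joint test it names would still not protect 2a and 2b.

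Four further points limit the size.
- A reader might infer that the functional claims carry a false-positive rate of up to about 25%. That figure counts any one of six two-sided pairwise differences, including differences against the device or against one comparator only. Neither kind would support 2a or 2b. Held to their wording, the claims are falsely made about 1-2% of the time under no effect, and about 5-8% in the least favourable case. However, the plan does not tie a claim to both contrasts, so that protection is not in its analysis text.
- A reader might also infer that a promised 5% level is broken. The only alpha belongs to the sample-size calculation, and no familywise level is promised for the secondaries.
- The plan does not assume an effect above 1 SD. It says "we have taken a very conservative estimate of effect size" and uses the lower bound. At that effect the joint test is not almost certain to be significant, although the family error remains about 13% with three outcomes.
- A reader might infer that the interaction wording itself inflates false device claims. Extra interaction tests bear on how often some follow-up is triggered. The natural reading is that a significant interaction is followed up as an interaction. The wording is loose, but no error rate for device claims follows from it.

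The remark that movement gains alone are insufficient is a rationale and not a decision rule; UE FM remains the single primary outcome.

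**Conclusion.** The point holds in limited form. The stated joint MANOVA gives no familywise protection to 2a and 2b once UE FM has an effect. If no adjustment is added and the univariate tests run at 0.05, at least one false secondary omnibus result occurs in about 9-10% of trials with the battery as one outcome and 11-15% with quality and time separate. Under the complete null it is about 3-4%. These are rates for the family; each single test stays at 5%. They rest on no true effect on the secondaries, 60 completers and assumed between-outcome correlations of 0 to 0.7.

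Separately, a significant omnibus test does not establish superiority to both comparators, so the stated test does not match the hypotheses. The primary analysis is not invalidated. This is an inexpensive improvement that should be made before the data are analysed.

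**What to change.** Replace the joint MANOVA as the entry to the secondary tests with this order:

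1. Test UE FM first, on its own.
2. Only if UE FM succeeds, test Box and Block, battery quality and battery time. For each, take the larger of the two p-values (MyoPro v splint, MyoPro v no device), and require both differences to favour the device.
3. Apply Holm's procedure to these three p-values at two-sided 0.05.
4. Label device-by-covariate interactions exploratory, and do not let them trigger tests of the device effect.

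This matches the wording of 2a and 2b and controls the family error across the three outcomes. It changes analysis wording only, with no new data, visits or participants. The cost is a somewhat stricter threshold for each secondary outcome: the smallest of the three p-values must meet 0.05/3 = 0.0167, the next 0.05/2 = 0.025 and the last 0.05.
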